[name], Study Coordinator, [name], [contact], [contact]

[name], Study Coordinator, [name], 1 [contact], [contact]

[name], Study Coordinator, [name], [contact], [contact]

[name], Research Assistant, GO Health Clinic, [name], [contact], [contact]

[name], Research Assistant, GO Health Clinic, [name], [contact], [contact]

[name], GO Health Clinic Manager [name], [contact], [contact]

[name], Statistician, [name], [contact], [contact]

[name]. Statistician (survey data), Howard W. Odum Institute for Research in Social Science, [name], 1 [contact], [contact]

PRÉCIS

Study Title

Antiviral Efficacy of Therapeutic Antiseptic Mouth Rinses for Inactivation of COVID SARS-2 Virus

Objectives

The primary objective is to quantify the impact of antiseptic mouthwashes on salivary infectivity in COVID-19+ patients. The secondary objective is to determine patients' acceptance of using antiseptic mouthwashes in healthcare settings.

Design and Outcomes

Randomized, double-blind prospective trial to test the efficacy and acceptability of two therapeutic, antiseptic mouth rinses to inactivate SARS-CoV-2 virus in saliva of COVID-19 positive patients aged 18-65 years old. Both mouth rinses are commercially available and will be used according to on-label instructions. Patients will be randomized to a mouth rinse and will be asked to give a saliva sample immediately before and after a one-minute mouthwash. Saliva samples will be collected from patients at 15-minute intervals thereafter up to an hour (15, 30, 45 and 60 minutes). The samples will be stored and used for RT-PCR detection of viral SARS-CoV-2 RNA and viral infectivity assays. Patients will also complete a short-survey on the taste and experience of using the mouthwash. This study involves one, 75-90 minute visit.

Interventions and Duration

Subjects will be asked to rinse with an unlabeled/blinded antiviral mouth rinse for 60 seconds and provide 5 mL of saliva prior to the rinse and 2 mL of saliva immediately post-rinse, 15 minutes post-rinse, 30 minutes post-rinse, 45 minutes post-rinse, and 60 minutes post-rinse. Subjects will also be asked to complete a short survey about the rinsing experience. Subjects will be onsite for a 70-90 minute, single visit appointment.

Sample Size and Population

We will enroll 84 COVID+ subjects per mouth rinse, with 3 mouth rinses (including a water control), requiring us to enroll 252 COVID+ patients. Patients will be

randomized to their selected mouth rinse assignment. These patients will have already had a confirmed COVID+ test within 10 days prior to enrollment. In addition to having a COVID+ test, patients will need to be at least 18 years of age and at most 65 years of age and in good oral health without any known allergies or reactions to the ingredients of the mouth rinses. Patients who are pregnant/ nursing/lactating, have a cognitive or developmental disability, have an active oral herpes flare up, have any oral viral infection and/or flare up, have significant mucosal tears, growths or damage to their mouth, have uncontrolled severe periodontal disease with bleeding gums, or have xerostomia will be excluded from the study. There is no exclusion criteria based on gender or race.

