2.2 Study Rationale

One promising strategy to reduce clinical spread is use of antiviral mouth rinses to inactivate SARS-CoV-2 infectability in saliva. Several commercially available mouth rinses have promising *in vitro* data with SARS-CoV-2 and *in vivo* data with other enveloped viruses, with a proposed mechanism of membrane disruption.^{3,11} Ethanol solutions (21% EtOH) have been shown to reduce SARS-CoV-2 viral infectivity levels *in vitro*, and in patients suffering Herpes Simplex Virus-1 flare-ups, a 30 second oral rinse significantly reduced salivary infectivity for over 30 minutes.¹² Cetylpyridinium chloride has promising *in vitro* data for inactivating SARS-CoV-2 infectivity.¹³ Minimal *in vivo* clinical data regarding SARS-CoV-2 exists to-date for most oral rinses.

Despite promising *in vitro* data, there is a dearth of *in vivo* clinical trials interrogating the efficacy of mouth rinses on reducing salivary SARS-CoV-2 viral infectivity. Given the rapid transmission and widespread distribution of the COVID-19 pandemic and its new variants, the development of protocols and treatments mitigating transmission represent a major and urgent unmet public health need; this study will rigorously address the *in vivo* utility of widely available oral rinses in limiting SARS-CoV-2 viral infectivity and their acceptability in the dental healthcare setting.⁵⁻⁸

Like other enveloped viruses, coronaviruses are surrounded by a lipid bilayer which allows for spike glycoproteins required for infection to be inserted.³ The mouth rinses proposed

in this study have shown success in previous studies in disrupting this lipid envelope in other viruses, and there is promise that they will do the same to the SARS-CoV-2 virus. Effect size: Based on our similar viral load studies evaluating mouth rinse efficacy against SARS-CoV-2 and studies about other enveloped viruses, we used power calculations to estimate effect size and determine sample size as a function of length of mouth rinse time course. With simultaneous comparisons across time points (T0-T1, T1-T2, T0-T2, T2-T3, T0-T3, T1-T3), the sample size $n=43$ for each mouth rinse can detect the effect size in Cohen's $d = 0.8$ at 30 minutes, which is between medium and large, under 80% power and 0.016 type-I error rate by Bonferroni correction.¹² To account for 14% of patients having no virus in their saliva and 10% of patient producing insufficient saliva, we plan to enroll 55 participants per arm.

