Participants will be asked to give a baseline salivary sample (5ml over 5 minutes) and then asked to rinse with an unlabeled (blinded) antiseptic mouth rinse for 60 seconds according to the table below. The rinses and control will be similar in appearance visually, such that a double-blind can be maintained. The research assistant ([name]) will be the sole unblinded staff member who will perform randomization and communicate the subject's group assignment to blinded study staff, in advance of the visit based on the block randomization schedule. The unblinded staff member will set-up the rinses for the participants appointment minimizing the possibility of study staff being able to identify the blinded rinses. In the instance that [name] is unavailable, [name] or [name] will perform randomization and set-up the rinses. Blind will be strictly maintained except in the case of medical emergency requiring reveal of an individual's rinse identity. The product group key will be provided to the analyzing statistician at the conclusion of the clinical study.

mouth rinse*	Number of participants (sample size)	Group
26.9% ethanol plus essential oils	84	Experimental
0.1% Cetylpyridinium Chloride	84	Experimental
Sterile water	84	Control

**All mouth rinses are commercially available in the USA, routinely used in clinical settings, and will be used in an on-label manner.*

After the participant expectorates the mouth rinse, research staff will collect another salivary sample (T_0 , 2 mL over 5 minutes). During a 10 minute recuperation period, the study participants will answer demographics survey questions and questions regarding the taste, color, flavor and general acceptability of using the mouth rinse as part of routine dental and medical visits as well as in social settings. At 15 minutes post-rinse, the participant will be asked to provide an additional saliva sample (2 mL over 5 minutes), followed by another 10 minute recuperation period. This sequence will be repeated for at

the 30, 45 and 60-minute time points post rinse. At 60 minutes, the study participant will give their final salivary sample (2 mL over 5 min), and study participation will conclude.

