9. STATISTICAL CONSIDERATIONS

9.1 General Design Issues

A double-blinded, randomized controlled trial was chosen as the study design. It allows us to collect human based data on the effects of commercially available mouth rinses on salivary infectivity and viral load. A crossover study was not pursued because the repeated use of different mouth rinses is likely to confound the results. A 1-hour time-course was chosen to correspond with the average length of most dental procedures. Fifteen minute intervals were chosen to evaluate viral kinetics over time, and to see when infectivity rebounds post- mouth rinse.

Statistical Hypothesis

The central hypothesis of this study is that a 60 second antiseptic mouth rinse will effectively reduce viral infectivity (>50%) of SARS-CoV-2 for a minimum of 30 minutes duration.

The secondary hypothesis is that a 60 second mouth rinse will be well tolerated in a clinical care setting by a majority of patients and providers.

Sample Size Considerations

Based on our similar viral load studies evaluating mouth rinse efficacy against SARS-CoV-2 and other enveloped viruses, we used power calculations to estimate effect size and determine sample size as a function of length of mouth rinse time course.¹² With simultaneous comparisons, the sample size n=43 for each mouth rinse can detect the effect size in Cohen's $d = 0.8$, which is between medium and large, under 80% power and 0.016 type-I error rate by Bonferroni correction.¹² To account for 14% of patients having no virus in their saliva and 10% of patients producing insufficient saliva, we plan to enroll 55 participants per arm.

Statistical analysis of our deidentified data will be performed by [name], the statistician on this project.

Primary Outcomes

The analyses will compare viral RNA level (qRT-PCR) and viral infectivity levels between mouth rinse types and across the time course

Data generated from the qRT-PCR assays will be presented as mean standard deviation for normally distributed data and as median [Interquartile range] for non-normally distributed data. P values will be reported as two tailed. Between group comparisons will be performed using a Student's t test or Mann-Whitney U test. Normality will be assessed using the Kolmogorov-Smirnov test, and logistic regression will be performed with robust standard errors.

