9.2 Sample Size and Randomization

Based on similar viral infectivity studies evaluating antiviral mouth rinse efficacy, we were able to run power calculations to estimate effect size and determine sample size as a function of length of mouth rinse time course. The sample size is justified by a paired t-test on outcomes between time points. With simultaneous comparisons, the sample size n=43 for each mouth rinse can detect the effect size in Cohen's $d = 0.8$ at 30 minutes, which is between medium and large, under 80% power and 0.016 type-I error rate by Bonferroni correction.¹² To account for 14% of patients having no virus in their saliva and 10% of patients producing insufficient saliva, we plan to enroll 55 participants per arm.

The statistical consultant on this project will create a block randomization tool for the study staff; the unblinded staff member will randomize a participant once enrollment compliance has been confirmed and consent has been given. The participant's group assignment will then be communicated to the blinded study staff. IRB approved study personnel will ask participants screening questions to confirm eligibility for enrollment. After consent and screening, the randomization tool will be used by study staff to assign the subject to a study group.

The researcher responsible for collecting the salivary samples will be blinded to the mouthwash solution, as they will be given a pre-aliquoted mouth rinse in an unlabeled tube to provide to the patient for the rinse.

The PI, Co-I, study coordinators and study personnel who work for GoHealth are authorized to break the blinding based on emergency medical necessity such as if a patient suffers an allergic or adverse reaction to one of the mouth rinses. Though highly unlikely as all mouth rinses are sold commercially at Walgreens and CVS, adverse or allergic reactions are possible. Using the numerical code associated with the participant and mouth rinse syringe, the study personnel responding to the emergency can reference the block randomization schedule to determine the mouth rinse type, to inform the emergency medical workers, poison control or the emergency room what type of mouth rinse product led to the reaction.

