Power Calculation: Based on our similar viral load studies evaluating mouth rinse efficacy against SARS-COV-2 and other enveloped viruses, we used power calculations to estimate effect size and determine sample size as a function of length of mouth rinse time course.¹² The sample size is justified by a paired t-test on outcomes between time points. With simultaneous comparisons, the sample size n=43 for each mouth rinse can detect the effect size in Cohen's d =0.8, which is between medium and large, under 80% power and 0.016 type-I error rate by Bonferroni correction.¹² To account for 14% of patients having no virus in their saliva, we plan to enroll 55 participants per arm. Analyses will compare viral RNA level (qRT-PCR) and viral infectivity levels between mouth rinse types and across the time course. ANCOVA models will be utilized to look at changes in viral load and infectivity logarithmically before and after treatment.

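### Enrolment is set at 84 per arm (252 in total) in the précis and design table but at 55 per arm in the power paragraph; nothing derives 84, and the n = 43 behind the 55 does not match its own stated inputs.

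*Combined protocol and SAP*

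**What the plan says.** Two places give 84 per arm. The précis (Sample Size and Population) states: "We will enroll 84 COVID+ subjects per mouth rinse, with 3 mouth rinses (including a water control), requiring us to enroll 252 COVID+ patients". The table of rinses in section 3 has a column headed "Number of participants (sample size" with 84 in each of its three rows. The 252 in the précis is the only total printed anywhere.

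Four places give 55 per arm, each at the end of a near-identical power paragraph:
- Section 2.2: "10% of patient producing insufficient saliva, we plan to enroll 55 participants per arm".
- Section 9.1 (Sample Size Considerations): "10% of patients producing insufficient saliva, we plan to enroll 55 participants per arm".
- Section 9.2 uses the same wording as 9.1.
- Section 9.5 (Power Calculation) drops the saliva allowance: "To account for 14% of patients having no virus in their saliva, we plan to enroll 55 participants per arm".

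The paragraph starts from n = 43 for each rinse and Cohen's d = 0.8, "under 80% power and 0.016 type-I error rate by Bonferroni correction". Sections 9.2 and 9.5 name the test: "The sample size is justified by a paired t-test on outcomes between time points". Section 2.2 alone lists the contrasts: "With simultaneous comparisons across time points (T0-T1, T1-T2, T0-T2, T2-T3, T0-T3, T1-T3), the sample size". Sections 9.1 and 9.5 make P values two-tailed.

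**The concern.** Both 84 and 55 are described as numbers to enrol, so they cannot be read as an enrolled and an evaluable count. None of the six statements is in an amendment log. Section 9.2, where a reader would look for the sample size, gives 55, while the précis and the allocation table give 84. Someone citing the plan could call enrolment complete at either number, and a later reader could not say whether the trial reached its planned size.

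The power paragraph is the only justification for any sample size. It leads to 55 and not to 84, and its own figure of 43 is not what its inputs produce. The plan therefore gives no checkable basis for the larger target and a doubtful one for the smaller.

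**Working it through.** **Inputs.** 84 per arm and 252 in total (précis); 84 per arm (section 3 table); 55 per arm (sections 2.2, 9.1, 9.2, 9.5); n = 43, d = 0.8, 80% power, alpha 0.016 (the same four sections); paired t-test (9.2, 9.5); six time contrasts (2.2); losses of 14% and 10% (2.2, 9.1, 9.2) or 14% only (9.5); two-sided tests (9.1, 9.5).

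**1. Totals.** 3 × 84 = 252, as printed. 3 × 55 = 165, which is not printed. 252 − 165 = 87.

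**2. From 43 to 55.** With both losses, 0.86 × 0.90 = 0.774 and 43/0.774 = 55.6. This is the plan's 55 within rounding (55 × 0.774 = 42.6). With the 14% loss alone, as in section 9.5, 43/0.86 = 50, which does not give 55.

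**3. From 43 to 84.** The loss needed is 1 − 43/84 = 0.488, or 49%. Treating 55 as the evaluable number does not help: 55/0.774 = 71. In the other direction, 84 × 0.774 = 65 evaluable, a number the plan does not mention.

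**4. The n = 43.** Power comes from the noncentral t distribution, two-sided, at alpha 0.016. The paired test has n − 1 degrees of freedom and noncentrality dz√n. If d is on the SD of the differences, dz = d. If d is on the raw SD with correlation r between time points, dz = d/√(2(1 − r)). The two-sample test has 2n − 2 degrees of freedom and noncentrality d√(n/2).

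| Reading (d = 0.8, alpha 0.016) | n for 80% power | Power at n = 43 |
|---|---|---|
| Paired, d on SD of differences | 20 | 99.6% |
| Paired, raw SD, r = 0.25 (dz = 0.653) | 28 | 96% |
| Paired, raw SD, r = 0 (dz = 0.566) | 36 | 88% |
| Paired, raw SD, r = −0.2 (dz = 0.516) | 43 | 80% |
| Two-sample t, n per arm | 35 | 89% |

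On the raw-SD scale with r = 0.5, dz is again 0.8 and the first row applies.

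**5. Nearest matches to 43.** At the stated alpha of 0.016 the paired test needs 43 only on the raw-SD scale with a correlation of about −0.2, an assumption the plan does not state. At alpha 0.05/6 with raw SD and r = 0 it needs 42, and 43 gives 82%, but that is not the stated alpha.

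**6. The alpha.** No family-wise level is given. Assuming 0.05, three comparisons give 0.05/3 = 0.0167, which truncates to 0.016. The six contrasts in section 2.2 would give 0.05/6 = 0.0083.

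**The case against.** The best defence is that the plan does favour one number. The 252 is the only printed total, the allocation table agrees with it, and the 55 sits in one paragraph copied into four sections, so that paragraph may simply not have been updated. That may be so, but no passage says it, and one of the copies is the section headed Sample Size and Randomization. The documents do not settle which target holds.

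A second defence is that the power statement is true as a statement of sufficiency: if 20, 35 or 36 is enough, so is 43. This stands against any charge of inadequate size. It does not explain why 43 is paired with 80% power. The statement also does not say how d is standardised, and only two of the four copies name the paired test. For the alpha, 0.05/3 is an obvious candidate in a three-rinse trial, so 0.016 has a plausible origin. What is missing is agreement with the six contrasts listed.

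A reader might infer that the trial is underpowered. The documents do not support that. At the stated alpha of 0.016, 43 gives at least 80% power in every reading above and falls short only on the raw-SD scale with a correlation below about −0.21. A reader might also infer that the missing power statement for the between-rinse comparison is part of the error. It is useful detail that the plan omits, but any figure for it would rest on an alpha the plan does not give.

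**Conclusion.** The contradiction between 84 and 55 per arm is an error in the current text, and it must be fixed on that ground alone: 252 against 165, or 87 participants. The stated losses lead from 43 to about 55, and nothing in the plan leads to 84.

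The n = 43 does not follow from the test, effect size, alpha and power printed beside it. The named paired test needs 20 or 36, depending on how d is scaled (the 36 assumes zero correlation), and a two-sample test needs 35. Matching 43 takes an unstated negative correlation, or coming within one of it takes a different alpha. These results assume two-sided t-tests and d = 0.8 as stated. The comparison of 0.016 with 0.0083 also assumes a family-wise level of 0.05. The mismatch runs in the conservative direction in the usual readings, so what is shown is an unreconciled target and a calculation that does not match its inputs, not a lack of power.

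**What to change.** 1. State one enrolment target, per arm and in total, in the précis, the section 3 table and sections 2.2, 9.1, 9.2 and 9.5, with the evaluable number and the losses that lead to it. Which of the two stated targets holds is for the sponsor to confirm.
2. Restate the power paragraph so that the test, the scale of d (with the correlation, if d is on the raw SD), the number of contrasts, the alpha, n and power agree. One way is to give the power that the confirmed evaluable number delivers for d = 0.8 under the named test.
3. Use the same loss allowance in all four copies. Section 9.5 names 14% only, which gives 50 and not 55.

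The cost is small but is more than wording: the statistician has to confirm the target, the alpha and the contrast count, and the stated power figure will change.

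Optional, and not part of the error: state a detectable difference for the between-rinse comparison, and say how the 10% saliva allowance relates to the replacement of participants in sections 6.2.5, 8 and 10.3.3.

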1. STUDY OBJECTIVES

1.1 Primary Objective

The primary objective of this study is to determine the efficacy of antiseptic mouthwashes on reducing SARS-CoV-2 cellular infectivity in COVID+ patient saliva. *We hypothesize that COVID-19+ patients will have a >95% reduction in SARS-CoV-2 viral infectivity following a 60 second oral rinse with an antiseptic mouth rinse and that this reduction will persist for at least 30 minutes.* This primary objective will focus on quantifying SARS-CoV-2 viral infectivity and RNA level using an *in vitro* infectivity assay and quantitative real time PCR. This objective provides urgently needed data to guide healthcare workers on the proper use of specific commercially available mouthwashes capable of reducing SARS-CoV-2 viral infectivity and potentially limiting COVID-19+ transmission.

1.2 Secondary Objectives

There is no secondary objective.

1.3 Tertiary Objectives

The tertiary objective is to determine the acceptability of using antiseptic mouthwashes on reducing SARS-CoV-2 cellular infectivity by patients in various settings including healthcare contexts. *We hypothesize that patients will welcome the use of commercially available antiseptic mouth rinses into clinical practice.* All patients enrolled will be surveyed on the taste, appearance, sensation, and acceptability of using the mouth rinse in different settings. Understanding acceptability of a mouth rinse protocol is critical to implementation and therefore the ability to reduce COVID-19 transmission risk in clinical settings.

2. BACKGROUND AND RATIONALE

2.1 Background on Condition, Disease, or Other Primary Study Focus

The COVID-19 global pandemic, caused by SARS-CoV-2 virus, represents a public health emergency with severe societal and economic impacts. Evaluating the potential for antiviral mouth rinses to inactivate SARS-CoV2 holds great potential for quelling the virus' spread among healthcare workers, who comprised up to 10% of COVID-19 cases early in the pandemic.^{1,2} Healthcare providers like dentists, who deliver care in and near the oropharynx, suffer the highest risk of occupational exposure, if using inadequate PPE.³ This is because SARS-CoV-2 is transmitted primarily through aerosol and respiratory droplets and salivary glands are a site of early SARS-CoV-2 viral replication and transmission.^{4,5} Dentists work in close proximity to the mouth and nasal passages with many procedures producing salivary airborne particles, particularly those involving ultrasonic and rotary instruments (hand pieces, “drills”) and 3-way syringes.⁵⁻⁸ High rates of SARS-CoV-2 transmission suggest that the minimum infectious dose is low compared to other viral diseases, and recent data suggest even one viral particle may be sufficient for infection.⁹ Working in close proximity to the oropharynx and generating salivary aerosols increases viral load exposure and therefore the risk of infection among dentists, oral surgeons, and other interventional doctors of the face.⁹ Furthermore, the proclivity of aerosols to remain airborne for up to 3 hours puts other patients, providers and staff at risk of exposure during aerosol-generating procedures, particularly in open bay clinics common to dental schools and large practices.^{4-6,10}

One promising strategy to reduce clinical spread is use of antiviral mouth rinses to inactivate SARS-CoV-2 infectability in saliva. Several commercially available mouth rinses have promising *in vitro* data with SARS-CoV-2 and *in vivo* data with other enveloped viruses, with a proposed mechanism of membrane disruption.^{3,11} Ethanol solutions (21% EtOH) have been shown to reduce SARS-CoV-2 viral infectivity levels *in vitro*, and in patients suffering Herpes Simplex Virus-1 flare-ups, a 30 second oral rinse significantly reduced salivary infectivity for over 30 minutes.¹² Cetylpyridinium chloride

